| Study Objectives | 
The primary objective is to evaluate the effectiveness of using a COPD clinical pathway compared to usual care among patients with an acute COPD exacerbation, on 60-day post discharge utilization (ED, inpatient, and observation encounters)
 
The secondary objectives are to examine the COPD clinical pathway's effect on additional patient outcomes, such as the
 
 a. CHS Quality, Comfort, and Care 30-day readmission rate. This is a readmission rate among patients with an inpatient readmission to the same CHS facility as the index encounter. b. The patient-centric 30-day readmission rate. This is a readmission rate among patients with an inpatient or observation readmission to any CHS facility. c. The patient-centric 30-day readmission rate where the primary diagnosis of the readmission is COPD. d. Length of stay e. Rate of follow-up visit within 5 days of discharge. f. Antibiotic order rate during admission g. Steroid order rate during admission h. Short acting bronchodilator order rate during admission 
Additional analyses will be to explore:
 
 a. The methodology for identification of COPD exacerbation within the first 24 hours of hospital admission will be compared to retrospective identification through billing codes. b. As a sub-analysis, qualitative outcomes will be collected and measured with patients, providers, and leaders. These outcomes will be collected and evaluated, per a sub-study protocol addendum. |
| Study Population | 
Patients 40 years of age or older hospitalized with an acute exacerbation of COPD are included. An acute exacerbation is defined as an encounter where the following criteria are met within 24 hours of admission.
 
 • The use of the COPD PowerPlan or • A respiratory therapy navigator notification of COPD exacerbation or • The use of the respiratory therapy department COPD bronchodilator protocol or |

| | |
|-------------------------|--|
| | 
• A historical diagnosis of COPD or A history of COPD in the admitting documentation or A COPD diagnosis on the problem list AND An order of systemic steroids (prednisone or methylprednisolone) 
For the purposes of this project, the evaluable population will include patients who meet the same age criteria and have a discharge diagnosis of acute exacerbation of COPD
 |
| Study Procedures | 
During this project, patients who are hospitalized at select CHS sites with COPD acute exacerbation symptoms will be treated per the CHS COPD clinical pathway (COPD Pathway). The COPD clinical pathway will include four components: (i) discrete, evidence-based care steps (ii) patient navigation, (iii) daily data driven care gap identification, (iv) monthly leadership huddles.
 
The evidence based care steps include: (1) verification of COPD diagnosis and severity, (2) patient/caregiver education regarding COPD and basic self-management skills, (3) standard pharmacologic bundle of systemic steroids, empiric antibiotics, bronchodilators, (4) pneumococcal and influenza vaccination review and completion, (5) smoking cessation advice and therapy when appropriate, (6) comprehensive care management assessment, (7) recommendations for pulmonary consultation, (8) recommendations for palliative care consultation, (9) use of discharge checklist, (10) recommendations for content of outpatient follow-up, and will be driven primarily by provider utilization of a comprehensive order-set that includes each component and a discharge checklist.
 
Patient navigation will be provided by the COPD Pathway Coordinator (COPD Coordinator) at each site. This role will be filled by an individual (s) who already exists on a site's care team. Because of this, the COPD Coordinator's site role and background may vary by site. The COPD Coordinators will be responsible for daily monitoring of care gaps that exist for COPD patients and their respective sites and alerting appropriate team member to help close those gaps. The COPD Coordinators will receive a daily COPD Gaps list. The COPD Gaps list identifies patients who are hospitalized at that time and the associated gaps in receiving the evidence based care components.
 
The intervention occurs at the site level and sites are randomized to the order they will receive the intervention in clusters of two. Two additional facilities will be added on a rolling basis in 2 month intervals, until all 8 facilities are active in using the COPD pathway. Once added, sites will begin utilizing the COPD Pathway in their daily practice.
 
As a part of the COPD clinical pathway, patients will meet the following discharge checklist criteria:
 
• On a long acting bronchodilator for 24 hours• A short acting bronchodilator is scheduled no more frequently than 4 times daily for 24 hours |

| | |
|-----------------------------|--|
| | 
• Be off IV steroids for 24 hours prior to discharge• A steroid prescription, or have completed a 5-day course while admitted• An antibiotic prescribed or have completed a 5-day course while admitted• A scheduled appointment with a care provider within 5 days of discharge• Received COPD education during discharge |
| Statistical Analysis | Analyses is among patients identified as having an acute exacerbation of COPD based on final billed coding. Comparisons of patients hospitalized during the intervention and usual care periods will be made using generalized estimating equations to control for clustering within hospital and repeated measures within hospital. The primary outcome, 60-day utilization, will be compared between the two groups of patients using a logit link in the generalized estimating equations. Results will be presented with odds ratios and 95% confidence intervals. |
| Sample Size Analysis | 8 hospitals will be randomized to intervention in 2 facilities per 2 month increments. With the assumption of detecting a change in rates of 60-day non-elective acute care utilization from 43% in the control period to 33% in the intervention period, 59 patients with COPD exacerbation per hospital per two months is needed to achieve a power of 0.80 (intra-class correlation coefficients (ICC)=0.05 and two-side $\alpha=0.05$). To account for this varying cluster size, we inflated the number of patients by 25% resulting in an average of 74 patients per hospital per two months, resulting in a total sample size of 2960 patients among the intervention group. |

LIST OF ABBREVIATIONS

| | |
|------|---------------------------------------|
| AE | Adverse Event or Acute Exacerbation |
| CHS | Carolinas Healthcare System |
| COPD | Chronic Obstructive Pulmonary Disease |
| EHR | Electronic Health Record |
| ED | Emergency Department |
| PHI | Private Health Information |
| PI | Principal Investigator |
| qid | 4 times per day |

TABLE OF CONTENTS

| | |
|--|------------------------------|
| 1. OBJECTIVES | ERROR! BOOKMARK NOT DEFINED. |
| 1.1. Hypothesis | 10 |
| 1.2. Primary Objective | 10 |
| 1.3. Secondary Objectives | 10 |
| 2. BACKGROUND | 10 |
| 3. RATIONALE | 10 |
| 4. SUBJECT AND SITE SELECTION | 11 |
| 4.1. Accrual..... | 11 |
| 4.2. Subjects..... | 11 |
| 4.3. Participating Sites..... | 12 |
| 4.4. Inclusion/Exclusion Criteria | 12 |
| 4.5. Evaluable Population..... | 13 |

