5.2 Trial Design

5.2.1 Justification for stepped wedge cluster randomized control trial

The primary aim is to assess the effectiveness of a structured multidisciplinary care plans (intervention), compared with standard care (control) on 60-day non-elective acute care utilization (ED visits, observation, and inpatient encounters). The COPD clinical pathway will be delivered at the level of hospital or cluster, thus minimizing contamination and the risk of selection bias, if subjects were randomized at the individual level¹². Therefore, the unit of randomization and

analysis for this study will be the cluster. Considering logistical constraints and design rigor, the intervention will be rolled out sequentially instead of at the same time. Moreover, substantial and differential cluster-effects may exist because of distinct volume and characteristics of patients in each hospital. Thus, the stepped wedge design is advantageous compared with other alternative designs.

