5.2.2 Randomization and allocation

The stepped wedge design implies a baseline period, in which no clusters are exposed to the intervention¹². Then, at the chosen time interval of two months, two hospitals will be randomized to cross from the control to intervention (**Figure 1**). This process continues until all eight hospitals have crossed over to the intervention. The order of this cross over process will be randomized. We will use block randomization to assign two hospitals at a time to switch from the control to intervention using SAS Enterprise Guide version 6.1. Allocation will be communicated only to hospital senior leadership initially to prevent contamination. Others including providers at the hospital will learn of allocation in the month preceding roll-out. Patients in included hospitals will be blinded to the intervention or control period.

[figure not shown]
Figure 1. The stepped wedge study design

| | 1-Apr | 1-Jun | 1-Aug | 1-Oct | 1-Dec | |
|-----------|-------|-------|-------|-------|-------|-----------------------------|
| Cluster 1 | 0 | 1 | 1 | 1 | 1 | 0=control 1=intervention |
| Cluster 2 | 0 | 1 | 1 | 1 | 1 | |
| Cluster 3 | 0 | 0 | 1 | 1 | 1 | |
| Cluster 4 | 0 | 0 | 1 | 1 | 1 | |
| Cluster 5 | 0 | 0 | 0 | 1 | 1 | |
| Cluster 6 | 0 | 0 | 0 | 1 | 1 | |
| Cluster 7 | 0 | 0 | 0 | 0 | 1 | |
| Cluster 8 | 0 | 0 | 0 | 0 | 1 | |

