5.2.5 Primary aim

The primary outcome for this study is 60-day non-elective acute care utilization. Characteristics of the hospitals and individuals will be summarized by levels of randomization steps, hospitals and individuals. The count, rates and 95% confidence intervals of 60-day non-elective acute care utilization in the -control period will be presented and compared with that in the -treatment period. The primary analysis will be conducted using generalized estimating equations with fixed effects for intervention, time (steps), and intervention multiply by the time, accounting for the cluster randomized trial design with a random cluster (hospitals) effect. We will estimate and report the intra class correlation coefficients for all outcome measures to assess assumptions for sample size analyses and for future investigations using similar designs and outcomes. The primary analyses will follow the intention to treat principle with an additional per protocol analysis including by using denominator in those who had pathway ordered as well as intervention periods when truly occurred. The secondary analyses will include within cluster comparisons of intervention and control periods (not adjusting for any confounding effect of time), as well as comparisons of a series of (unbalanced) quasi-parallel cluster trials between those enrolled and unenrolled clusters at each intervention enrollment period. The same analyses plan will also be applied to secondary outcomes.

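### The primary GEE on 8 hospitals fixes neither its variance estimator and reference distribution nor the contrast that is the primary odds ratio; on the customary GEE reading its 5% test has about 14-15% type I error

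*Combined protocol and SAP*

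**What the plan says.** The statistical analysis row of the synopsis compares intervention and usual-care periods "using generalized estimating equations to control for clustering within hospital and repeated measures within hospital", with a logit link for the primary outcome. It adds: "Results will be presented with odds ratios and 95% confidence intervals".

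Section 5.2.5 gives the model in more detail. Its terms are set out as "generalized estimating equations with fixed effects for intervention, time (steps), and intervention multiply by the time". Hospitals come into the same model through a further phrase, which describes it as "accounting for the cluster randomized trial design with a random cluster (hospitals) effect". The section promises estimated intra-class correlations, and then states: "The same analyses plan will also be applied to secondary outcomes".

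Section 5.2.1 makes the hospital both the unit that is randomized and the unit that is analysed ("analysis for this study will be the cluster"). Section 5.2.2 has two hospitals cross over every two months: "This process continues until all eight hospitals have crossed over to the intervention". There are therefore 8 independent units. Section 5.2.3 gives power 0.80 at 59 patients per hospital per two months, raised to 74 for unequal hospital sizes.

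Neither the synopsis nor sections 5.2.3 to 5.2.6 mention a variance estimator, a small-sample correction, a reference distribution or a permutation test. A working correlation is not named either, although the random hospital effect and the single ICC point towards an exchangeable one.

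**The concern.** A GEE is usually reported with the robust (sandwich) standard error and a normal reference. That combination relies on many clusters. With 8, the robust standard error is too small on average and is itself variable, so p-values are too low and intervals too narrow. A random hospital effect is not a component of a GEE, so section 5.2.5 can also be read as asking for model-based errors. The two readings have different error rates, and the text does not choose between them.

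The interaction adds a second gap. Once intervention-by-time is in the model there is no single intervention odds ratio, and the plan does not say which combination of coefficients is primary. Two analysts could follow the text faithfully and report different primary odds ratios and p-values.

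Section 3 says the evaluation is meant to guide system strategy on a resource-intensive programme. On the customary reading, an ineffective pathway would be declared different from usual care about one time in seven. If the choice is made after the data are seen, it becomes a choice of primary p-value.

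**Working it through.** **Inputs from the documents.** Section 5.2.2, Figure 1: 8 hospitals, 5 two-month periods, two hospitals crossing at each of 4 steps. Section 5.2.3: 43% versus 33%, ICC 0.05, two-sided 5%, 59 per hospital-period raised to 74, sizes 30 to 158, CV about 0.5.

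**Assumptions not in the documents.** Hospital effects are normal. Unequal sizes are 30, 40, 50, 60, 70, 84, 100 and 158 (mean 74). Where drift is mentioned, 20% of the between-hospital variance is hospital-by-period.

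**Step 1: reproduce the plan's 59.** The Hussey-Hughes variance, with I = 8, T = 5 and s = within-hospital variance / n, is

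Var = I·s·(s + T·τ²) / [(I·U − W)·s + (U² + I·T·U − T·W − I·V)·τ²].

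- Figure 1 gives U = 20, W = 0 + 4 + 16 + 36 + 64 = 120 and V = 2 × (16 + 9 + 4 + 1) = 60.
- I·U − W = 160 − 120 = 40. The second bracket is 400 + 800 − 600 − 480 = 120.
- Total variance 0.43 × 0.57 = 0.2451, so τ² = 0.05 × 0.2451 = 0.012255 and s = 0.95 × 0.2451 / 59 = 0.003947.
- Var = 8 × 0.003947 × (0.003947 + 0.061275) / (40 × 0.003947 + 120 × 0.012255) = 0.001264. The SE is 0.0356 and 0.10 / SE = 2.81.
- Normal reference: Φ(2.81 − 1.96) = 0.80, and 59 is the smallest size that reaches 0.80. The plan's figure is reproduced.
- Same ratio with t on 6 df (critical value 2.447): power 0.65. At 74 the ratio is 3.14, giving 0.88 with a normal reference and 0.74 with t on 6 df.

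**Step 2: type I error by reading.** Null simulations of the logit GEE on the Figure 1 layout: rate 43%, 74 per cell (equal and unequal sizes), ICC 0.05, intervention plus categorical period, exchangeable correlation.

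| Variance and reference | Hospital effects constant | With drift |
|---|---|---|
| Robust, normal | about 14-15% | about 14-16% |
| Robust, t on 6 df | about 8-9% | not needed here |
| Model-based, normal | about 5.5-6.5% | about 12-14% (single runs to about 15%) |
| Kauermann-Carroll, t on 6 df | about 4-6% | about 4-6% |
| Permutation of roll-out order | about 5% | not quoted here |

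Interval coverage under the first row is 100 − 14 = 86% to 100 − 15 = 85%.

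The size of the first row can be checked by hand. The mean robust SE of the log odds ratio was 0.109, against a true standard deviation of 0.133 to 0.137. The effective critical value is then 1.96 × 0.109 / 0.133 = 1.61 to 1.96 × 0.109 / 0.137 = 1.56, which gives about 11-12%. Variability of the SE across trials supplies the rest.

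**Step 3: the contrast.** Five periods times two conditions make 10 combinations. Period 1 has no intervention and period 5 has no control, so 8 are observed. With categorical steps, a period-specific effect exists only in periods 2, 3 and 4. With robust errors and a normal reference:

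- linear interaction, evaluated at the middle step: 15.8-17.2%;
- categorical, period 3: 14.6-16.4%;
- categorical, period 2 or 4: 22.0-25.0%. Here even Kauermann-Carroll with t on 6 df gives 9.6-11.0%.

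With model-based errors and constant hospital effects, every contrast tried gave 4.8-6.7%.

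**Step 4: simulated power at 43% versus 33%, constant hospital effects.** Kauermann-Carroll with t on 6 df: about 0.65-0.67 at 59 and about 0.73-0.78 at 74, in line with step 1. Permutation test: 0.73-0.77 at 59 and 0.82-0.85 at 74.

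**Step 5: the patient total.** 74 × 8 × 5 = 2,960 fills all 40 cells of Figure 1. Intervention cells number 2 × (4 + 3 + 2 + 1) = 20, and 20 × 74 = 1,480. The figure 5920 is 2 × 2,960.

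**The case against.** The strongest defence is that section 5.2.5 is the most specific text. Its random hospital effect, with the single ICC of section 5.2.3, describes an exchangeable or random-intercept model, and with model-based errors that model is close to nominal. This stands as far as it goes: the plan admits a sound reading and is under-specified rather than shown to be invalid. But the reading is sound only if hospital effects stay constant over five periods, and the synopsis and section 5.2.5 both name GEE, for which robust errors are customary.

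Several stronger inferences are tempting and are not supported.

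- A reader might quote 5.5% to 20% as the range over readings. It is not. About 20% needs an independence working correlation with unequal sizes (19.9%), the reading that section 5.2.5 supports least, while some interaction contrasts exceed 20%.
- A reader might infer that the error rate depends on the contrast under any reading. Step 3 shows this is mainly a robust-SE result. Under model-based errors with constant effects, the missing contrast is an ambiguity about what is estimated.
- The drift figures rest on an assumed share of variance and show sensitivity only.
- A reader might carry the figures to all secondary outcomes because the same analysis is applied there. Only a binary outcome at about 43% was examined; length of stay is not binary, and the order rates may have very different prevalence.

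It is also fair that removing the interaction from the primary model is a preference. Naming the contrast would close that gap.

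**Conclusion.** The point holds: the plan does not determine the error rate of its primary test or which odds ratio is primary. Under the customary GEE reading the 5% test runs at about 14-15%. Under the model-based reading it runs at about 5.5-6.5% if hospital effects are constant, and about 12-14% under the assumed 20% drift. These figures rest on the plan's own layout, rates, ICC and cluster sizes, with normally distributed hospital effects, and apply to the primary outcome. The 0.80 at 59 is a normal-reference figure, so a small-sample-valid analysis has less power than stated at that size. This should be settled before the data are seen.

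The label on 2960 is a separate numerical error with no bearing on the error rate.

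**What to change.** 1. **Method.** In the synopsis and section 5.2.5, pre-specify one small-sample-valid method that gives both the p-value and the 95% interval. One option is exchangeable GEE with Kauermann-Carroll variance and t on 6 df (8 hospitals minus 2). Another is a permutation test over the 8!/(2!)⁴ = 2,520 roll-out orders (only the allowed orders if randomization was restricted), with the interval obtained by inverting the same test.
2. **Contrast.** Name one. The simplest is the intervention coefficient from the model with intervention and categorical period. If the interaction stays in the primary model, state the contrast and confirm that the chosen method holds its error rate for it.
3. **Power.** In section 5.2.3, restate power for the chosen method. Section 4.1 sets no accrual target, so enrolment does not change.
4. **Separate correction.** In the synopsis and section 5.2.3, relabel 2960 as the total over all cells (1,480 intervention), and explain what 5920 includes; sections 1.3 and 4.2 mention historical data.

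**Cost.** Plan wording and some code, with no extra patients. Relative to the uncorrected robust interval, intervals widen by about 44-48% with Kauermann-Carroll and t on 6 df, or about 29-34% with the inverted permutation test. The first option brings stated power at 74 to about 0.73-0.78. The second keeps 0.82-0.85 under the plan's assumptions but needs more programming.

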1. OBJECTIVES

1.1. Hypothesis

Patients with an acute COPD exacerbation, who receive care at a site using the COPD clinical pathway, will have lower 60-day post discharge utilization than patients that receive usual care.

1.2. Primary Objective

The primary objective is to evaluate the effectiveness of the use of the COPD clinical pathway compared to usual care, on 60-day post discharge utilization (ED, inpatient, observation encounters) among patients with an acute COPD exacerbation.

1.3. Secondary Objectives

- a. The secondary objectives are to examine the COPD clinical pathway's effect on additional patient outcomes, such as the
 - i. CHS Quality, Comfort, and Care 30-day readmission rate. This is a readmission rate among patients with an inpatient readmission to the same CHS facility as the index encounter.
 - ii. The patient-centric 30-day readmission rate. This is a readmission rate among patients with an inpatient or observation readmission to any CHS facility.
- b. The methodology for identification of COPD exacerbation within the first 24 hours of hospital admission will be compared to retrospective identification through billing codes.
- c. Demographics and comorbid conditions will be characterized among the historical population of patients at CHS with COPD exacerbation.

2. BACKGROUND

Chronic Obstructive Pulmonary Disease (COPD) is a disease characterized by persistent respiratory symptoms, incompletely reversible expiratory airflow obstruction, intermittent episodes of acute airway and alveolar inflammation termed exacerbations. COPD is hallmark with periods of symptom stability, and periodic acute deteriorations of the patient's disease condition, called exacerbations. Acute COPD exacerbations frequently lead to ED utilization and/or hospitalization in acute care facilities¹. Reported COPD costs in the U.S. have reached approximately \$37 billion annually, with hospitalizations accounting for most the estimated costs, and are only expected to continue rising. Prior to implementation of the CMS Hospital Readmission Reduction Program, approximately 20% of patients admitted to a hospital for AECOPD were readmitted (all cause) within 30 days. Other types of acute care utilization following hospital admission (ED visits, Urgent Care encounters, hospital observation stays have not been studied². Less stringent definitions of care utilization including readmission and ED and/or Urgent Care encounters further than 30 days out, can safely be assumed to be even worse.

With the advent of value based care, and the rise of bundled payments for a single episode or cycle of care, it has become increasingly important to devise innovative care delivery systems and pathways that will both treat patients effectively in the acute setting and prevent readmissions. Further haste driving

innovation and work in this disease state, has been Medicare's identification of COPD as a target for the Hospital Readmission Reduction Program. This program penalizes hospitals for 30-day readmissions among patients for specific index encounters, such as those with COPD³.

Development and implementation of new acute COPD care models will cost significant investment of time and capital. Such investment and the need to have a valid assessment of benefit, necessitate strategic, a priori evaluation planning and execution prior to widespread implementation.

Healthcare systems are increasingly adopting disease specific Clinical Pathways (CPW's). These pathways are structured, multidisciplinary care plans, often inclusive of order sets, that detail necessary care steps for patients with a specific disease. Despite being present since the 1980's and fairly ubiquitous in many hospitals since the early 2000's, they have a limited evidence base. A 2011 Cochrane review could not draw conclusions on their effects on length of stay and cost, due to variability in study designs. However, review of the resulting data did show reduced hospital complications (OR 0.58; 95% CI 0.36-0.94). Another review showed that a 3-month integrated disease management intervention (multidisciplinary, multi-faceted care) among inpatients was beneficial with 15 patients needing to be treated to eliminate 1 respiratory related hospital admission⁴⁻⁷. Particularly in the transition to value based care models, there remains an obligation for further research to prove effectiveness and cost efficacy for care pathways.

There have been ongoing efforts to define the COPD population based on biologic factors, clinical characteristics, and social determinants of health to help identify patients at risk for exacerbations, hospital admission, hospital readmission, and mortality. Some factors associated with increased risk of hospital readmission include congestive heart failure, behavioral health issues, medical frailty, increasing age, and (simply) prior admission for a COPD exacerbation^{3,8}. Predictive models and scoring systems have been devised, most commonly using dyspnea scores, measurements of expiratory airflow limitation, previous hospitalizations, age, and chronic comorbidities; however, use of these tools has not been proven to reduce acute healthcare utilization. Attempts at care pathways for delivery of standardized intervention for acute COPD exacerbations and complex care interventions for patients with COPD have produced equivocal results and there is lack of consensus as to whether such clinical care pathways convincingly improve overall patient outcomes.

Even as improvements are made in terms of the understanding of the COPD population, and risk factors for readmission, the optimal method to reduce utilization remains questionable. Attempts at care pathways nationwide, and other interventions for COPD patients have been undertaken with mixed reports of success. The state of research is best summarized by noting that, while several intermediate or process-oriented outcomes (such as patient self-report of ability to manage symptoms or number of follow-up phone calls made to patients) have been impacted by efforts to improve coordination of care, studies to date have yet to convincingly illustrate an improvement in utilization rates after any such intervention⁹⁻¹¹.

